5. INVESTIGATIONAL PLAN

5.1 Summary of Study Design

This is a multicenter, open-label, Phase III study that will evaluate the efficacy and safety of OKZ in subjects with moderately to severely active RA who previously completed 24 weeks of double-blind treatment in Study CL04041022, CL04041023, or CL04041025.

This study will be conducted at approximately 250 global sites across Russia, Belarus, the US, Europe, the United Kingdom (UK), Asia, and Latin America. It is estimated that approximately 1880 subjects will be enrolled.

Subjects will be assessed for eligibility to enter the study at Visit 1 (which is the same visit as the Week 24 visit of the core studies), and eligible subjects will be assigned to 1 of 2 dosing frequencies (q2w or q4w) of 64 mg OKZ as described in Section 5.2.

[figure not shown]
The study will consist of an 82-week open-label Treatment Period, with the last dose of OKZ being administered at Week 104. After completion of the open-label Treatment Period, subjects will come to Visit 10 (End of Treatment [EoT]/Week 106) 2 weeks after the last dose of OKZ for scheduled safety and efficacy assessments. After Visit 10 (EoT/Week 106), subjects will be scheduled for Safety Follow-Up Visits SFU-1 (Week 108), SFU-2 (Week 112), and SFU-3 (Week 126) to perform adequate safety assessments.

The total amount of time to complete the OLE study will be approximately 102 weeks (inclusive of the open-label Treatment Period and the Safety Follow-Up Period). The total amount of time to complete both the core study and the OLE study will be approximately 130 weeks (2.5 years) (inclusive of the Screening, double-blind Treatment Period, open-label Treatment Period, and Safety Follow-Up Period).

Subjects who discontinue treatment prematurely will be required to come to Visit 10 (EoT/Week 106) 2 weeks after the last dose of study treatment for scheduled efficacy and safety assessments. These subjects will subsequently be followed for an additional 20 weeks (i.e., 22 weeks after the final dose of study treatment) during a Safety Follow-Up Period.

A schematic of the study design is presented in Figure 1. The Schedule of Events to be conducted during the 82-week open-label Treatment Period (Week 24 through Week 106) and the Safety Follow-Up Period (Week 106 through Week 126) is presented in Table 1.

Figure 1 CL04041024 (CREDO 4) Study Schematic

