5.4.3 Safety Follow-Up: Visits SFU-1, SFU-2, and SFU-3

5.4.3.1 Visit SFU-1 (Week 108 or 4 Weeks after the Last Dose of the Study Treatment)

The following assessments will be conducted 4 weeks after the last dose of the study treatment:

- Record AEs/SAEs.
- Record details of contraceptive history/status.
- Record concomitant medications and concomitant non-drug therapies.
- Record weight.
- Record vital signs.
- Perform partial physical examination.
- Measure ESR.
- Collect sample to measure CRP level.
- Collect samples for chemistry panel and hematology assessments.
- Perform urine pregnancy test for females of childbearing potential only.

5.4.3.2 Visit SFU-2 (Week 112 or 8 Weeks after the Last Dose of the Study Treatment)

The following assessments will be conducted 8 weeks after the last dose of the study treatment:

- Record AEs/SAEs.
- Record details of contraceptive history/status.
- Record concomitant medications and concomitant non-drug therapies.
- Administer TB risk questionnaire.
- Record weight.
- Record vital signs.
- Perform partial physical examination.
- Measure ESR.
- Collect sample to measure CRP level.

- Collect samples for chemistry panel and hematology assessments.
- Perform urine pregnancy test for females of childbearing potential only.

5.4.3.3 Visit SFU-3 (Week 126 or 22 Weeks after the Last Dose of the Study Treatment)

The following assessments will be conducted 22 weeks after the last dose of the study treatment:

- Record AEs/SAEs
- Record details of contraceptive history/status.
- Record concomitant medications and concomitant non-drug therapies.
- Record weight.
- Record vital signs.
- Perform complete physical examination.
- Perform 12-lead ECG.
- Collect samples for INR, aPTT, and fibrinogen.
- Collect samples for lipid panel and CV risk panel.
- Collect samples for chemistry panel, hematology assessments, ANAs, and dsDNA antibodies.
- Perform urine pregnancy test for females of childbearing potential only.
- Collect sample for urinalysis.

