7.4.1.1 Eliciting Adverse Event Information

A consistent methodology of non-directive questioning should be adopted for eliciting AE information at all subject evaluation time points. Examples of nondirective questions from the Investigator to the subject include the following:

- "How have you felt since your last clinic visit?"
- "Have you had any new or changed health problems since you were last here?"

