7.4.5.4 Follow-up of Adverse Events

Any AEs that occur at or after Visit 1 (OLE Baseline/Week 24) until the end of the Safety Follow-Up Period (i.e., 22 weeks after the last dose of study treatment) will be followed up to resolution. Resolution means that the subject has returned to a baseline state of health, the Investigator does not expect any further improvement or worsening of the AE, or the subject is lost to follow-up. The Investigator should follow each SAE until the event is resolved or returned to the baseline, the event is assessed as stable by the Investigator, the subject is lost to follow-up, or the subject withdraws consent. For AEs with a causal relationship to the study treatment, R-Pharm International or its designee must concur with the Investigator's assessment.

For SAEs, nonserious AESIs, and pregnancies, R-Pharm International's designee may follow-up by telephone, fax, electronic mail, and/or a monitoring visit to obtain additional case details and outcome information (e.g., from hospital discharge summaries, consultant

reports, or autopsy reports) in order to perform an independent medical assessment of the reported case.

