7.4.9 Tuberculosis Risk Questionnaire

The questionnaire "Tuberculosis Risk Questionnaire" (see Appendix 2 [Section 13.2]) should be used as a source document. The questionnaire will be completed at Visits 1 (OLE Baseline/Week 24), 4 (Week 36), 6 (Week 52), 8 (Week 76), 10 (EoT/Week 106), and SFU-2 (Week 112) as noted in Table 1.

If question No. 1 (Does the subject have a new diagnosis of active TB disease) of the TB risk questionnaire is answered with "Yes" at Visit 1 (OLE Baseline/Week 24), the subject is not allowed to enter the study (see exclusion criterion No. 2, Section 5.3.2). A "Yes" response to any of the other questions within the questionnaire at Screening should trigger further careful assessment to determine the subject's risk of TB disease.

At any visit after Visit 1 (OLE Baseline/Week 24), a "Yes" response should be treated as follows:

- Question 1: If a subject answers "Yes" study treatment should be discontinued if active TB is confirmed (see Section 6.11).
- Questions 2 through 6: If a subject answers "Yes" to any question, they should be assessed (TB risk questionnaire and physical examination) 12 weeks from the time of exposure to determine if the subject developed TB. The Investigator should consult with a certified TB specialist or pulmonologist, if needed.
 - Questions 7 through 12: If a subject answers "Yes" to any question, this should trigger a careful assessment to determine if the subject developed TB (see Section 7.4.10).

This risk questionnaire is not to be used to exclude TB disease or confirm diagnosis.

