13.2 Appendix 2: Tuberculosis Risk Questionnaire

The following questions are to be asked to every subject for evaluation of signs and symptoms of tuberculosis (TB). Responses to each question must be documented on this source document.

Question	Response
1) Does the subject have a new diagnosis of TB disease?	□ Yes □ No
2) Has the subject been in close contact (i.e., sharing the same household or other enclosed environment, such as a social gathering place, workplace, or facility, for extended periods during the day) with an individual with active TB since the last scheduled visit?	□ Yes □ No
3) Has the subject become an employee at a TB hospital, forensic medical examiner, or morgue since the last scheduled visit?	□ Yes □ No
4) Has the subject started work or has the subject stayed in long-stay institutions (e.g., homes for elderly or disabled, prisons, etc) since the last scheduled visit?	□ Yes □ No
5) Does the subject reside in or is the subject frequently travelling to a TB endemic region (as defined in Table 5)? (only applicable for subjects not living in an endemic region)	☐ Yes ☐ No ☐Not applicable
6) Has the subject been in frequent contact with underprivileged populations (homeless people or other people needing social assistance) since the last scheduled visit?	□ Yes □ No
7) Does the subject have a new cough lasting more than 14 days or a change in a chronic cough?	□ Yes □ No
8) Does the subject have night sweats?	\square Yes \square No
9) Does the subject have a persistent fever?	\square Yes \square No
10) Does the subject have unintentional weight loss (more than 10% of body weight) in the past 3 months?	□ Yes □ No
11) Does the subject appear malnourished?	\square Yes \square No
12) Has the subject had an abnormal chest X-ray since the last evaluation?	□ Yes □ No
Physician's signature:	

Table 5 List of Endemic TB Countries (Incidence >50/100,000)

Country	Incidence ^a	Country	Incidence ^a	Country	Incidence ^a
Afghanistan	189 (167–212)	Greenland	197 (173–223)	Nigeria	322 (189–488)
Algeria	78 (64–94)	Guatemala	57 (51–64)	Northern Mariana Islands	61 (53–69)
Angola	370 (240–529)	Guinea	177 (156–199)	Pakistan	270 (201–350)
Azerbaijan	77 (68–86)	Guinea-Bissau	369 (261–495)	Papua New Guinea	417 (304–547)
Bangladesh	227 (200–256)	Guyana	103 (91–116)	Peru	120 (98–145)
Belarus	58 (50–67)	Haiti	200 (177–225)	Philippines	288 (254–324)
Benin	61 (50–74)	India	167 (156–179)	Romania	81 (71–91)
Bhutan	164 (148–181)	Indonesia	399 (274–546)	Russia	84 (76–93)

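### The TB questionnaire's exposure questions look back only to the previous scheduled visit, so up to 38 of 88 weeks may never be asked about (0 on a lenient reading); a smaller gap is that the form is not scheduled at SFU-3

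*Combined protocol and SAP*

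**What the plan says.** **Schedule.** Section 7.4.9 names Visits 1, 4 and 6 (Weeks 24, 36 and 52), followed by Visits "8 (Week 76), 10 (EoT/Week 106), and SFU-2 (Week 112) as noted in Table 1". The Table 1 row shows the same visits. Section 5.4.3.3 introduces its list for SFU-3 with "The following assessments will be conducted 22 weeks after the last dose of the study treatment". That list includes adverse event recording, weight, vital signs and a complete physical examination, but not the questionnaire. The three places agree. Interferon-gamma release assay testing and chest X-ray are last scheduled at Week 106.

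**Questions.** In Appendix 2, Question 2 asks about close contact "with an individual with active TB since the last scheduled visit". Questions 3, 4 and 6 use the same look-back. Question 5 (endemic regions) is in the present tense and has none. Symptom questions include Question 7: "Does the subject have a new cough lasting more than 14 days or a change in a chronic cough".

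**Actions.** Under 7.4.9, a positive answer to any of Questions 2 to 6 leads to a repeat questionnaire and a physical examination 12 weeks after the exposure. For a positive answer to Questions 7 to 12, "this should trigger a careful assessment to determine if the subject developed TB".

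**Other routes.** Section 7.4.1.1 says: "A consistent methodology of non-directive questioning should be adopted for eliciting AE information". Section 7.4.3.1 requires subjects to be told to contact their physician at once about any symptom suggesting infection. Under 7.4.5.4, adverse events arising "until the end of the Safety Follow-Up Period (i.e., 22 weeks after the last dose of study treatment) will be followed up to resolution".

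**The concern.** The exposure questions are tied to the visit calendar, but the form is given at only some visits. Each time a visit without the form falls between two forms, a literal reader asks only about the time since that visit. The weeks between the earlier form and that visit are then covered by neither form. An exposure in those weeks is not recorded and cannot start the 12-week assessment, which is the main purpose of the exposure questions.

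The second issue is the end of follow-up. After Week 112 no form is routinely scheduled, so a prolonged or changed cough (Question 7) or night sweats (Question 8) at SFU-3 would have to be volunteered in answer to open questions. A positive answer there could still be acted on, because events arising up to the end of follow-up are followed to resolution.

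TB is a named adverse event of special interest (7.4.3). Section 5.1 states: "This study will be conducted at approximately 250 global sites across Russia, Belarus, the US, Europe". Russia and Belarus are both on the protocol's own endemic list (Table 5: 84 and 58 per 100,000).

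**Working it through.** The plan gives no figure for this, so the check is calendar arithmetic on nominal weeks.

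**Inputs.** Scheduled visits (Table 1): Weeks 24, 26, 28, 36, 44, 52, 64, 76, 88, 106, 108, 112, 126. Questionnaire (Table 1, 7.4.9): Weeks 24, 36, 52, 76, 106, 112. The Week 24 form looks back into the core study and is left out.

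**Literal look-back, Questions 2, 3, 4 and 6.** For each form, weeks asked about = form week − previous scheduled visit. Weeks skipped = previous scheduled visit − previous form week.

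| Form at week | Previous scheduled visit | Weeks asked about | Weeks skipped |
|---|---|---|---|
| 36 | 28 | 36 − 28 = 8 | 28 − 24 = 4 |
| 52 | 44 | 52 − 44 = 8 | 44 − 36 = 8 |
| 76 | 64 | 76 − 64 = 12 | 64 − 52 = 12 |
| 106 | 88 | 106 − 88 = 18 | 88 − 76 = 12 |
| 112 | 108 | 112 − 108 = 4 | 108 − 106 = 2 |
| Total | | 50 | 38 |

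Check: 50 + 38 = 88 = 112 − 24. The skipped share is 38/88 = 43%. Of the 38 weeks, 4 + 8 + 12 + 12 = 36 fall in the 82-week Treatment Period.

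**Lenient look-back.** If the phrase means the last visit at which the form was given, each form reaches back to the one before it and the skipped total is 0. The range is therefore 0 to 38 weeks.

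**End of follow-up.** 126 − 112 = 14 weeks, or 12 to 16 with the ±7-day window at each end. That is 14 of the 20 Safety Follow-Up weeks. For early discontinuers it is the same: 22 − 8 = 14 weeks.

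**Triggered repeats after Week 112.** Exposures in Weeks 100–106 reported at Visit 10 fall due at Weeks 112–118. Exposures in Weeks 108–112 reported at SFU-2 fall due at Weeks 120–124. Some subjects will therefore see the form again after Week 112.

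**What a form at SFU-3 could do.** The visit before SFU-3 is Week 112, which has the form, so even a literal look-back would cover Weeks 112–126 in full. The 12-week date is within the study only for exposures up to 126 − 12 = Week 114. Exposures in the last 12 of the 14 weeks could be recorded but not reassessed in the study.

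**Effect of the edits.** The SFU-3 form alone closes the 14 weeks and leaves the 38 unchanged. The new look-back wording alone reduces the 38 to 0. The longest recall period then becomes 106 − 76 = 30 weeks.

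**The case against.** **The schedule is a consistent choice.** Table 1, 5.4.3.3 and 7.4.9 agree, and three of the intervals between forms during treatment (16, 24 and 30 weeks) are longer than the 14 weeks at the end. This stands: the absence at SFU-3 is not an inconsistency. The final interval differs only in that no later form closes it.

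**The look-back has a sensible reading.** A form used at selected visits may be meant to refer to the last such visit, and Question 12 on the same form refers to the last evaluation. This is why 38 is an upper bound. However, Section 5.5 uses the term scheduled visit for all of Visits 2 to 9, including those without the form, so the literal reading is also the protocol's own usage.

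**TB detection does not stop at Week 112.** A reader might infer that it does. The documents do not support that. SFU-3 has adverse event recording, under which confirmed active TB is a serious event, and a complete examination that includes the respiratory system and lymph nodes. Subjects are told to report infection symptoms immediately, and one sample prompt in 7.4.1.1 asks about new or changed health problems. These overlap much of the form. What loses a direct prompt is mainly Questions 7 and 8.

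**The form has limited use by SFU-3.** Section 7.4.9 says it neither excludes nor confirms TB. Subjects are then about 5 half-lives past the last dose, so there is no dosing decision left. This also stands and limits the gain to prompting a work-up.

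**A larger combined figure is tempting.** Adding 38 and 14 gives 52 of 102 weeks (51.0%). That total takes the literal reading as certain and counts closing weeks in which the exposure questions would add little, so it should not be used.

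**Conclusion.** The point holds as a minor one, in two parts.

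The look-back wording is the more substantive part. Between 0 and 38 of the 88 weeks from Week 24 to Week 112 go unasked, depending on how sites read one phrase. The count applies to Questions 2, 3, 4 and 6 only, and to a subject who completes treatment at nominal visit weeks.

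The SFU-3 part is small. Apart from triggered 12-week repeats, no structured TB symptom questions follow Week 112, and the remaining procedures cover part of the loss.

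A reader might infer missed TB cases or understated rates of special-interest events. The documents support neither. The figures count weeks without a direct question, and the number of cases affected cannot be estimated from what is given.

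**What to change.** **Look-back.** In Appendix 2, Questions 2, 3, 4 and 6, replace the reference to the previous scheduled visit with *since the last TB risk questionnaire*. This removes the ambiguity and closes the 38 weeks without adding a form. The cost is a longer recall period, up to 30 weeks (Week 76 to Week 106).

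**SFU-3.** Add the existing questionnaire at Week 126 in Table 1, 5.4.3.3 and 7.4.9, mainly for Questions 7 to 12. It also serves as a backstop if a 12-week repeat after Visit 10 or SFU-2 was missed. That repeat should otherwise stay at its due date, by an Unscheduled Visit (5.4.4) if needed. The cost is one 12-question form per subject at an existing visit and a few extra work-ups. Exposures after Week 114 would still not reach their 12-week assessment within the study.

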7.4.10 Management of Tuberculosis

Subjects that develop evidence of latent or active TB once enrolled in the study (and receiving study treatment) must immediately discontinue further administration of study treatment, and the subject should be examined by certified TB specialist or pulmonologist who is familiar with diagnosing and treating TB (as acceptable per local practice).

If active is confirmed, the subject must permanently discontinue study treatment (see Section 6.11). Confirmed active TB is an SAE that must be recorded on the relevant pages of the eCRF and provided to the Sponsor in accordance with SAE reporting requirements. Details regarding follow-up of SAEs are provided in Section 7.4.5.5.

If latent TB is confirmed, the subject may resume the administration of study treatment if active TB is ruled out by a certified TB specialist or pulmonologist who is familiar with diagnosing and treating TB (as acceptable per local practice), the subject starts prophylactic treatment of LTBI according to country-specific/CDC guidelines (see Appendix 4 [Section 13.4]), and the subject agrees to complete the entire course of recommended LTBI therapy. Study treatment should not be administered until active TB is ruled out, the subject starts prophylactic LTBI therapy, and the Investigator receives confirmation from the Medical Monitor if the subject deviated from the allowed injection window. Confirmed latent TB should be recorded as an AE on the relevant pages of the eCRF. Details regarding follow-up of AEs are provided in Section 7.4.5.4.

7.5 Appropriateness of Measurements

All assessments made in this study are standard, widely used, and generally recognized as reliable, accurate, and relevant.

8. QUALITY CONTROL AND QUALITY ASSURANCE

According to the Guidelines of Good Clinical Practice (GCP) (CHMP/International Council for Harmonisation [ICH]/135/1995), R-Pharm International and R-Pharm International's designee are responsible for implementing and maintaining quality assurance and quality control systems with written standard operating procedures (SOPs).

Quality control will be applied to each stage of data handling.

The following steps will be taken to ensure the accuracy, consistency, completeness, and reliability of the data:

- Investigator meetings
- Central laboratories for clinical laboratory parameters
- Study site initiation visit
- Early study site visits after enrollment
- Routine study site monitoring
- Ongoing study site communication and training
- Data management quality control checks
- Continuous data acquisition and cleaning
- Internal review of data
- Quality control check of the final clinical study report

In addition, R-Pharm International's (or designee's) Clinical Quality Assurance Department may conduct periodic audits of the study processes, including study site, study site visits, central laboratories, vendors, clinical database, and final clinical study report. When audits are conducted, access must be authorized for all study-related documents including medical history and concomitant medication documentation to R-Pharm International's designee and regulatory authorities.

8.1 Monitoring

R-Pharm's designee will perform all monitoring functions within this clinical study. The designee's monitors will work in accordance with established SOPs and have the same rights and responsibilities as monitors from R-Pharm International. Monitors will establish and maintain regular contact between the Investigator and R-Pharm International.

Monitors will evaluate the competence of each study site, informing R-Pharm International about any problems relating to facilities, technical equipment, or medical staff. During the study, monitors will check that written informed consent has been obtained from all subjects correctly and that data are recorded correctly and completely. Monitors are also entitled to compare entries in eCRFs with corresponding source data and to inform the Investigator of any errors or omissions. Monitors will also control adherence to the protocol at the study site. They will arrange for the supply of study treatment and ensure appropriate storage conditions are maintained.

Monitoring visits will be conducted according to all applicable regulatory requirements and standards. Regular monitoring visits will be made to each study site while subjects are enrolled in the study. The monitor will make written reports to R-Pharm International on each occasion contact with the Investigator is made, regardless of whether it is by phone or in person.

During monitoring visits, entries in the eCRFs will be compared with the original source documents (source data verification).

For further details of study monitoring, please refer to the Clinical Operations Plan and the Pharmacy Monitoring Guidelines.

Data Management/Coding

Data generated within this clinical study will be handled according to the relevant SOPs of the Data Management and Biostatistics departments of R-Pharm International's designee.

An EDC system will be used for this study, meaning that all eCRF data will be entered in electronic forms at the study site. Data collection will be completed by authorized study site staff designated by the Investigator. Appropriate training and security measures will be completed with the Investigator and all authorized study site staff prior to the study being initiated and any data being entered into the system for any study subjects.

All data must be entered in English. The eCRFs should always reflect the latest observations on the subjects participating in the study. Therefore, the eCRFs are to be completed as soon as possible during or after the subject's visit. To avoid interobserver variability, every effort should be made to ensure that the same individual who made the initial baseline determinations completes all efficacy and safety evaluations. The Investigator must verify that all data entries in the eCRFs are accurate and correct. If some assessments are not done, or if certain information is not available or not applicable or unknown, the Investigator should indicate this in the eCRF. The Investigator will be required to electronically sign off on the clinical data.

Electronic case report form records will be automatically appended with the identification of the creator, by means of their unique User ID. Specified records will be electronically signed by the Investigator to document his/her review of the data and acknowledgement that the data are accurate. This will be facilitated by means of the Investigator's unique User ID and password; date and time stamps will be added automatically at the time of electronic signature. If an entry on an eCRF requires change, the correction should be made in accordance with the relevant software procedures. All changes will be fully recorded in a protected audit trail, and a reason for the change will be required.

The monitor will review the eCRFs and evaluate them for completeness and consistency. The eCRF will be compared with the source documents to ensure that there are no discrepancies between critical data. All entries, corrections, and alterations are to be made by the responsible Investigator or his/her designee. The monitor cannot enter data in the eCRFs. Once clinical data of the eCRF have been submitted to the central server, corrections to the data fields will be audit trailed, meaning that the reason for change, the name of the person who performed the change, together with time and date will be logged. Roles and rights of the study site staff responsible for entering the clinical data into the eCRF will be determined in advance. If additional corrections are needed, the responsible monitor or Data Manager will raise a query in the EDC application. The appropriate study site staff will answer queries sent to the Investigator. This will be audit trailed by the EDC application meaning that the name of study site staff, time, and date stamp are captured.

The eCRF is essentially considered a data entry form and should not constitute the original (or source) medical records unless otherwise specified. Source documents are all documents used by the Investigator or hospital that relate to the subject's medical history, that verify the existence of the subject, the inclusion and exclusion criteria, and all records covering the subject's participation in the study. They include laboratory notes, ECG results, memoranda, pharmacy dispensing records, subject files, etc.

The Investigator is responsible for maintaining source documents. These will be made available for inspection by the monitor at each monitoring visit. The Investigator must submit a completed eCRF for each subject who receives study treatment, regardless of duration. All supportive documentation submitted with the eCRF, such as laboratory or hospital records, should be clearly identified with the study and subject number. Any personal information, including subject name, should be removed or rendered illegible to preserve individual confidentiality.

Adverse events and medical history will be coded using the most recent version of the Medical Dictionary for Regulatory Activities (MedDRA). Concomitant medications will be coded using the World Health Organization Drug Dictionary Enhanced (WHO DDE).

